**Table 1: Clinical Laboratory Evaluations** 

Biochemistry	Albumin (ALB)	
	Alkaline phosphatase (ALP)	Lactate dehydrogenase (LDH)
	Alanine aminotransferase (ALT; SGPT)	Protein
	Aspartate aminotransferase (AST; SGOT)	Magnesium (Mg)
	Blood urea nitrogen (BUN)	Potassium (K)
	C4	Uric acid

	Calcium (Ca)	Sodium (Na)
	Chloride (Cl)	Bicarbonate (CO2)
	Creatinine	Gamma glutamyl transferase (GGT)
	Creatine kinase	Glucose
	Phosphate (P)	Total and direct bilirubin
Coagulation	Activated partial thromboplastin time	International normalized ratio
	Prothrombin time	
Lipid Panel	Total Cholesterol	HDL Cholesterol
	LDL Cholesterol	Triglycerides
Endocrinology	Triodothyronine (T3)	Thyroid-stimulating hormone (TSH)
Hematology	Hemoglobin	Red blood cell (RBC)
	Hematocrit	White blood cell (WBC) count with differential
	Mean corpuscular hemoglobin (MCH)	Mean corpuscular volume (MCV)
	Platelets	Prothrombin time (PT)
	Activated partial thromboplastin time (aPTT)	International normalized ratio (INR)
Urinalysis	Appearance (clarity and color)	Microscopic examination of sediment
	Bilirubin	Nitrite
	Blood	рН
	Glucose	Protein
	Ketones	Specific gravity
	Leukocyte esterase	Oxalate
	Urobilinogen	
Other Lab Tests	Vitamin A	Vitamin D

Vitamin E	HbA1c
HOMA-IR	HOMA-%B

Clinical laboratory test values are potentially clinically important (PCI) if they meet either the low or high PCI criteria listed in Table 2. A supportive listing of subjects with post-baseline PCI values will be provided including the subject number, site, baseline, and post-baseline values.

Test Name	PCI Criteria
Chemistry Panel	
Albumin	<3g/dl
Alkaline phosphatase (ALP)	>5 x ULN
Transaminase, SGOT, AST	>5 x ULN
Transaminase, SGPT, ALT	>5 x ULN
ALT or AST in combination with other events	(1) ALT or AST >3xULN and (Total Bilirubin >2xULN or INR >1.5) at same visit
	or
	(2) ALT or AST >3xULN with the appearance of fatigue, nausea, vomiting, right upper quadrant pain or tenderness, fever, rash, and/or eosinophilia (>5%) at same visit
Blood Urea nitrogen (BUN)	>2.5 x ULN* (or alternatively H >30mg/dl**)
Calcium	<8mg/dl or >11.5mg/dl
Bicarbonate	<20 mEq/L or >30 mEq/L
Chloride	<90mEq/L or >110mEq/L
Creatinine, serum	>1.5 x ULN (or alternatively H >2mg/dl**)
Creatine Kinase	>1.5 x ULN
Gamma Glutamyl Transpeptidase (GGT)	>5 x ULN
Glucose, serum	<55mg/dl or >160mg/dl

Lactate dehydrogenase (LDH)	>3 x ULN*
Magnesium	<1.233mEq/L or >1.997mEq/L
Phosphorus, inorganic	<2.5mg/dl or >7.0mg/dl**
Potassium, serum/plasma	<3mEq/L (grade 3) or >5.5mEq/L
Sodium	<130mEq/L (grade 3) or >150mEq/L
Bilirubin, total	>2.0 x ULN
Direct bilirubin	>2.0 x ULN
Total protein, plasma or serum	<5g/dl* or >9g/dl*
Uric acid, serum / Urate	>8mg/dl
Endocrinology Panel	
Free T3/ Triodothyronine	< 1.4 pg/mL or > 7.5 pg/mL
Thyroid Stimulating Hormone (TSH) / Thyrotropin	<0.35 mIU/L or >6 mIU/L
Lipid Panel	
Total Cholesterol	<100mg/dL or ≥300mg/dl
HDL Cholesterol	≤40mg/dL
LDL Cholesterol	<50mg/dL or ≥150mg/dl
Triglycerides	>400mg/dL
Other Chemistry Tests	
Hemoglobin A1c	>0.09 Fraction of 1
Vitamin D, 25 Hydroxy	<12ng/mL

of 1

Basophils/Leukocytes	<0.15 Fraction of 1
Lymphocytes/Leukocytes	>0.80 Fraction of 1
Monocytes/Leukocytes	<0.40 Fraction of 1
Urinalysis	
Clarity	Any result other than clear
Color	Any results other than yellow
Bilirubin	Positive Value (excluding trace)
Blood / Occult Blood	Positive Value (excluding trace)
Glucose	Positive Value (excluding trace)
Ketones	Positive Value (excluding trace)
Leukocyte esterase	Positive Value (excluding trace)
Nitrite	Positive Value (excluding trace)
рН	<4.5 or >8
Protein	Positive Value (excluding trace)
Specific gravity	<1.005 or >1.025
Urobilinogen	>1 EU/dL
Microscopic Examination	
Red Blood Cells/Erythrocytes	≥ 5 /HPF
White Blood Cells/Leukocytes	≥ 5 /HPF
Bacteria	Any character value that is not "None" or
	"Rare" (or their equivalent)
Calcium oxalate crystals	Any present/positive (or equivalent)

LLN: Lower limit of normal value provided by the laboratory ULN: Upper limit of normal value provided by the laboratory

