## 10.3 Vital Signs

Descriptive statistics for vital signs (temperature, sitting blood pressure (systolic blood pressure, diastolic blood pressure), pulse, respiratory rate, weight, waist circumference and waist:hip ratio ) and their changes from baseline at each post-baseline visit and at the FoTA will be presented by treatment group. Vital signs data will be listed.

Vital sign values will be considered PCI if they meet the criteria listed in Table 3. A listing of subjects with post-baseline PCI values will be provided including the subject number, baseline, and post-baseline PCI values.

		Clinically Significant Vital Signs PCI Criteria	
Vital Sign Parameter	Flag	Observed Value	Change from Baseline
Systolic blood pressure	High	≥160	-
(mmHg)	Low	<90	-
Diastolic blood pressure	High	≥100	-
(mmHg)	Low	<60	-
Respiratory Rate	High	>25	-
(breaths per minute)	Low	<12	-
Pulse rate	High	≥110	-
(beats per minute)	Low	≤50	-
Weight (kg)	High	-	Increase of ≥5%
	Low	-	Decrease of ≥5%
Temperature (deg. C)	High	>39	-
	Low	<35	-

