## 10.4 Electrocardiogram (ECG)

Descriptive statistics for ECG variables (heart rate, PR, RR, QRS, QTc and QT intervals) and their changes from baseline at each assessment time point will be presented by treatment

\*The NCI has not specified a value, Shire physicians have agreed on lab values provided.

\*\* Values taken from the Reviewer Guidance, Conducting a Clinical Safety Review of a New Product Application and Preparing a Report on the Review, Table 7.1.7.3.2.1 pp 70-72. US DHHS FDA CDER, February 2005.

group. QTc interval will be calculated using both Bazett (QTcB=QT/(RR)1/2) and Fridericia (QTcF=QT/(RR)1/3) corrections; and if RR is not available, it will be replaced with 60/hr in the correction formula. A listing for 12-lead ECG results and interpretation by central reader.

Electrocardiogram variable values will be considered PCI if they meet or exceed the values listed in Table 4. A listing of all subjects with post-baseline PCI value will be provided including the subject number, baseline, and post-baseline PCI values.

Table 4: Criteria for Potentially Clinically Important ECG values			
ECG Parameter	Unit	PCI Criteria	ECG Parameter
ECG Result	-	-	Abnormal and
			clinically significant
			from investigator
Heart Rate	beats/minute	≤50	≥110
PR Interval	msec	-	≥220
QT Interval	msec	-	≥480
QTc Interval	msec	-	≥460 and <480
			$\geq$ 480 and $<$ 500
			≥500
QT/QTc increase	Msec	-	≥30 and <60
from baseline			≥60
QRS Interval	Msec	-	≥120

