## 14.4 Repeated or Unscheduled Assessments of Safety Parameters

Unscheduled visits will be mapped to a visit according to the visits window in Appendix 1.

If a subject has repeated assessments before the start of investigational product, then the results from the final assessment made prior to the start of investigational product will be used as baseline.

If a subject has repeated assessments after the start of investigational product within a visit window, only the scheduled visit will be used for efficacy analyses. For safety analyses, the results from scheduled visit will be used first, if no scheduled visit, the record from the visit closest to target date will be used. If there are multiple records with the same distance to the target date, the latest record will be used.

If the final on-treatment safety assessments are repeated or unscheduled, the last post-baseline assessment will be used as the final on-treatment assessment for generating descriptive statistics.

However, all post-baseline assessments will be used for PCI value determination and all assessments will be presented in the data listings.

26Jul2018

Page 33 of 43

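### PCI laboratory, vital-sign and ECG values are only listed: outside AST, ALT and total bilirubin, no by-arm count is planned, and most criteria do not separate new from pre-existing values

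*SAP*

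**What the plan says.** **Definition.** Section 10.2 sets the laboratory rule by threshold: "Clinical laboratory test values are potentially clinically important (PCI) if they meet either the low or high PCI criteria listed in" Table 2. Nothing in it depends on the subject's status before dosing. Two criteria elsewhere are relative to baseline: weight in Table 3 (for a gain, "Increase of ≥5" per cent, with a matching loss) and "QT/QTc increase" from baseline in Table 4. The other vital-sign and ECG criteria are not.

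**Output.** For laboratory tests: "A supportive listing of subjects with post-baseline PCI values will be provided including the subject number, site, baseline, and post-baseline values". For vital signs: "A listing of subjects with post-baseline PCI values will be provided including the subject number, baseline, and post-baseline PCI values". For ECG: "A listing of all subjects with post-baseline PCI value will be provided including the subject number, baseline, and post-baseline PCI values". These become Listings 8.1.3, 8.2.2 and 8.3.2 in section 17.2. The tables in section 17.1 include none on PCI values.

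**Which assessments count.** Section 14.4 treats PCI and the visit summaries differently. For PCI: "However, all post-baseline assessments will be used for PCI value determination and all assessments will be presented in the data listings". For visit rows: "For safety analyses, the results from scheduled visit will be used first, if no scheduled visit, the record from the visit closest to target date". If the final on-treatment assessment (FoTA) is repeated or unscheduled, the last value is taken.

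**What is summarised by arm.** Section 10.2 and Table 2.6.9 give AST, ALT and total bilirubin elevations by treatment group, including over the whole post-baseline period. An eDISH plot shows each subject's peak ALT and total bilirubin.

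**The concern.** The trial was stopped for lack of efficacy. The tables left in section 17.1 cover only subject characteristics and safety; biopsy, MRI and quality-of-life data are listed. The by-arm description of safety is therefore the main content of the abbreviated report.

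PCI is the only safety measure for which section 14.4 states outright that all post-baseline assessments count. It is also the measure with no by-arm summary. Outside AST, ALT and total bilirubin, no planned output shows how many subjects on each dose, and on placebo, newly reached a clinically important value.

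Section 10.1 does draw this distinction for adverse events: one that began before dosing is treatment-emergent only if it worsens afterwards. PCI values have no counterpart to that rule.

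**Working it through.** The SAP contains no figure to reproduce. The check compares its sections, followed by an illustration with assumed rates.

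**1. Planned outputs, section 10 against section 17**

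| Domain | PCI output | PCI count by arm | Other by-arm output |
|---|---|---|---|
| AST, ALT, total bilirubin | Listing 8.1.3 | None under the PCI label | Table 2.6.9, including overall post-baseline |
| Other laboratory tests | Listing 8.1.3 | None | Visit and FoTA descriptive statistics (2.6.1 to 2.6.8) |
| Vital signs | Listing 8.2.2 | None | Visit and FoTA descriptive statistics (2.7.1) |
| ECG | Listing 8.3.2 | None | Promised in section 10.4, but no ECG table in 17.1 |

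ALP, GGT and direct bilirubin have PCI thresholds in Table 2 but are not in Table 2.6.9, so they belong to the second row.

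**2. Path of an unscheduled extreme**

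- Appendix 1 sets the windows. Week 12 is days 72 to 127, which is 127 − 72 + 1 = 56 days. Week 24 is days 128 to 211, which is 211 − 128 + 1 = 84 days.
- Suppose a scheduled potassium on day 168 is normal, and an unscheduled one later in the same window exceeds 5.5 mEq/L, the Table 2 threshold.
- The Week 24 row uses the day 168 value.
- The unscheduled value enters the FoTA row only if it is the last on-treatment value. Being the worst value does not put it there.
- PCI determination captures it, but it then appears only in a listing.

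**3. Why a raw count from the listings would not be enough (purely illustrative)**

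Let b be the share already meeting a criterion at baseline, assumed to persist, and r the new-onset rate among the rest. The proportion with any post-baseline PCI value is b + (1 − b) × r. Every rate below is an assumption; none comes from the SAP. Take r = 5% on placebo and 10% on active, a new-onset ratio of 0.10 / 0.05 = 2.00.

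| b | Placebo | Active | Ratio |
|---|---|---|---|
| 0% | 0 + 1.00 × 0.05 = 5% | 0 + 1.00 × 0.10 = 10% | 2.00 |
| 20% | 0.20 + 0.80 × 0.05 = 24% | 0.20 + 0.80 × 0.10 = 28% | 1.17 |
| 40% | 0.40 + 0.60 × 0.05 = 43% | 0.40 + 0.60 × 0.10 = 46% | 1.07 |

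The SAP plans no such crude rate. The table shows only why an added count should be restricted to subjects who did not meet the criterion at baseline. With b = 0 the restriction changes nothing.

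**The case against.** The strongest reply is that listing-only PCI output is a coherent choice for an abbreviated report. Sections 10, 14.4 and 17 agree with one another on it, no inferential safety analysis is planned, adverse events are tabulated by arm, and the detailed output specifications are in a separate document that may add columns or flags. This stands, and it is why the point is not an error in the plan. It does not supply a by-arm count.

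Some stronger readings are tempting, but the SAP does not support them:

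- **PCI ignores baseline.** All three listings show the baseline value, and the weight and QT/QTc-increase criteria are changes from baseline. What is missing is a rule separating new from pre-existing values under the remaining criteria.
- **PCI is the only measure that reflects extremes.** Table 2.6.9 has an overall post-baseline summary and eDISH uses peaks. The SAP does not say whether these include unscheduled values, but it does not exclude them. Section 14.1 also puts the minimum and maximum in every continuous summary, so visit rows are not means alone. A maximum is still not a count of subjects, and it does not help with qualitative urinalysis results.
- **Arms cannot be compared.** Counts could be built by hand from the listings and the randomization listing (16.1.7). The accurate statement is that no tabulated comparison is planned.
- **Unscheduled values are lost from all by-arm tables.** FoTA can admit a last unscheduled value, and an unscheduled record can fill a window that has no scheduled visit.
- **The listings would mostly show existing metabolic disease.** Section 7 names BMI categories and T2DM as variables to summarise and gives no prevalence. Thresholds such as HDL of 40 mg/dL or below make some baseline abnormality conceivable, but the SAP does not say how much.

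**Conclusion.** The point holds as a cheap improvement. PCI values for laboratory tests other than AST, ALT and total bilirubin, and for vital signs and ECG, have no planned n and percentage by treatment group. Apart from weight and QT/QTc increase, the criteria do not separate newly arising values from those present before dosing. An intermediate unscheduled extreme that shares a window with a scheduled visit reaches no visit row.

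The gap is widest for ECG: unless the separate output specifications add a table, the listed outputs contain no by-arm ECG summary at all.

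The size cannot be stated from the SAP, which gives neither baseline prevalence nor frequency of PCI values. The fall in ratio from 2.00 to 1.17 or 1.07 rests wholly on assumed rates and on baseline abnormality persisting. It should not be read as an estimate for this trial.

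**What to change.** Add three descriptive tables to sections 10.2 to 10.4 and 17.1: laboratory tests other than AST, ALT and total bilirubin, vital signs, and ECG. Each gives n/N (%) of subjects by treatment group with a treatment-emergent PCI value, per criterion.

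- **Numerator:** subjects meeting the criterion at any post-baseline assessment, scheduled or unscheduled.
- **Denominator:** subjects with a baseline value that does not meet the criterion and at least one post-baseline value.
- **Change-from-baseline criteria** (weight, QT/QTc increase): used as they stand.
- **Two-sided or graded criteria:** low, high and each QTc band assessed separately, so that a move from a lower band to a higher one is counted.

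Flag subjects who met a criterion at baseline in Listings 8.1.3, 8.2.2 and 8.3.2. They leave the denominator for that criterion, so the flag keeps any further worsening visible.

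The cost is a short SAP amendment and three tables built from flags the listings already require. The downside is a slightly longer abbreviated report. No inferential analysis is added.

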## 10.3 Vital Signs

Descriptive statistics for vital signs (temperature, sitting blood pressure (systolic blood pressure, diastolic blood pressure), pulse, respiratory rate, weight, waist circumference and waist:hip ratio ) and their changes from baseline at each post-baseline visit and at the FoTA will be presented by treatment group. Vital signs data will be listed.

Vital sign values will be considered PCI if they meet the criteria listed in Table 3. A listing of subjects with post-baseline PCI values will be provided including the subject number, baseline, and post-baseline PCI values.

		Clinically Significant Vital Signs PCI Criteria	
Vital Sign Parameter	Flag	Observed Value	Change from Baseline
Systolic blood pressure	High	≥160	-
(mmHg)	Low	<90	-
Diastolic blood pressure	High	≥100	-
(mmHg)	Low	<60	-
Respiratory Rate	High	>25	-
(breaths per minute)	Low	<12	-
Pulse rate	High	≥110	-
(beats per minute)	Low	≤50	-
Weight (kg)	High	-	Increase of ≥5%
	Low	-	Decrease of ≥5%
Temperature (deg. C)	High	>39	-
	Low	<35	-

## 10.4 Electrocardiogram (ECG)

Descriptive statistics for ECG variables (heart rate, PR, RR, QRS, QTc and QT intervals) and their changes from baseline at each assessment time point will be presented by treatment

\*The NCI has not specified a value, Shire physicians have agreed on lab values provided.

\*\* Values taken from the Reviewer Guidance, Conducting a Clinical Safety Review of a New Product Application and Preparing a Report on the Review, Table 7.1.7.3.2.1 pp 70-72. US DHHS FDA CDER, February 2005.

group. QTc interval will be calculated using both Bazett (QTcB=QT/(RR)1/2) and Fridericia (QTcF=QT/(RR)1/3) corrections; and if RR is not available, it will be replaced with 60/hr in the correction formula. A listing for 12-lead ECG results and interpretation by central reader.

Electrocardiogram variable values will be considered PCI if they meet or exceed the values listed in Table 4. A listing of all subjects with post-baseline PCI value will be provided including the subject number, baseline, and post-baseline PCI values.

Table 4: Criteria for Potentially Clinically Important ECG values			
ECG Parameter	Unit	PCI Criteria	ECG Parameter
ECG Result	-	-	Abnormal and
			clinically significant
			from investigator
Heart Rate	beats/minute	≤50	≥110
PR Interval	msec	-	≥220
QT Interval	msec	-	≥480
QTc Interval	msec	-	≥460 and <480
			$\geq$ 480 and $<$ 500
			≥500
QT/QTc increase	Msec	-	≥30 and <60
from baseline			≥60
QRS Interval	Msec	-	≥120

## 10.5 Other Safety Variables

#### 10.5.1 Bristol Stool Chart

The Bristol Stool Chart (BSC) is a medical aid designed to classify the form of human feces into seven categories, where 1 is the hardest and 7 is the softest. Types 3 and 4 would be normal and types at either end of the scale would be severe. Stools will be assessed by the bowel movement consistency of the softess stool within the last 24 hours prior to the clinic visit. BSC responses on the rating scale of stool hardness (Type 1 to Type 7) will be listed by time point and treatment group. Summaries of stool hardness by time point and treatment group will be provided.

Stool frequency will be assessed by the number of bowel movements within the last 24 hours prior to the clinic visit. Summary statistics (number of observations, mean, SD, median, maximum, and minimum) will also be presented by treatment group for frequency of bowel movements by day. The stool frequency would be PCI if it is  $\geq$ 6 BM/day.

## 11. CLINICAL PHARMACOKINETIC AND PHARMACODYNAMIC ANALYSES

26Jul2018

Page 30 of 43

## 11.1 Pharmacokinetics Population and Pharmacodynamics Population

Pharmacokinetic data was not collected in this study. For pharmacodynamics population, see section 4.6.

## 11.2 Pharmacokinetic Methods

N/A

## 11.3 Statistical Analysis of Pharmacokinetic Data

N/A

#### 11.4 Pharmacodynamic Methods

BA synthesis will be assessed via alpha-hydroxy-4-cholesten-3-one [C4] concentrations.

## 11.5 Statistical Analysis of Pharmacodynamic Data

C4 concentration data will be listed.

## 12. OTHER ANALYSES

## **12.1** Health-related Quality of Life Analyses

All Health-related Quality of Life data will be listed for the full analysis set.

## 13. COMPUTER METHODS

Data analyses will be performed by ICON. Statistical analyses will be performed using Version 9.3 (or newer) of SAS® on a suitably qualified environment.

## 14. DATA HANDLING CONVENTIONS

## **14.1** General Data Reporting Conventions

Continuous variables will be summarized using the following descriptive statistics: n, mean, median, SD, minimum, maximum. The minimum and maximum values will be presented to the same number of decimal places as the raw data. The mean and median will be presented to one more decimal place than the raw data. The SD will be presented to two more decimal places than the raw data.

26Jul2018

Page 31 of 43

Categorical data and count variables will be summarized using n and percentages based on the number of non-missing values. Percentages will be presented to one decimal place. The number of missing values will be presented as a separate category with no percentage, but only if 1 or more patients are missing data for the summary. Otherwise, all categories will be presented (even if no patients are counted in the category). Counts of zero in any category will be presented without a percentage.

## 14.2 Derived Efficacy Endpoints

NAS, MRI-PDFF, HOMA-IR, and SAF will be derived in the dataset according to the rules in Appendix 2 of the protocol. If any of the individual components are missing, then the corresponding NAS, SAF, MRI and HOMA –IR will be set to missing.

MRI hepatic PDFF will be derived based on images from multi-echo (ME) and double echo (DDE) sequences.

will The **MRI** hepatic **PDFF** endpoint be derived in four ways: 1) The first analyzable ME result will be used at a visit. If the ME is not analyzable the DDE will be used at a visit. ME results are selected preferentially. If neither ME nor DDE is analyzable, a repeat will be requested and if repeat is requested then the result to use is based on the ME preferentially then the DDE on this repeated imaging. It is possible for the baseline to come from ME and week 24 to come from DDE and vice versa. This will be the primary definition of the MRI hepatic PDFF endpoint as suggested by the expert radiologist.

3) Use MRI hepatic PDFF only based on DDE images. Only those subjects with both an analyzable DDE at baseline and at week 24 and week 24 will be included in change from baseline analyses. 4) If ME is available at both baseline and week 24 then the MRI hepatic PDFF endpoint should be based on ME images. Otherwise, if DDE is available at both baseline and week 24 then the MRI hepatic PDFF endpoint should be based on DDE images.

## 14.3 Association of Early Termination Assessments to Scheduled Visits

For purposes of reporting early termination assessments during the study, each early termination visit will be mapped to a visit according to the visits window in Appendix 1. This rule applies to both efficacy variables (e.g., ALT) and safety variables (e.g., vital signs) that are analyzed and/or summarized by visit.

## 14.4 Repeated or Unscheduled Assessments of Safety Parameters

Unscheduled visits will be mapped to a visit according to the visits window in Appendix 1.

If a subject has repeated assessments before the start of investigational product, then the results from the final assessment made prior to the start of investigational product will be used as baseline.

If a subject has repeated assessments after the start of investigational product within a visit window, only the scheduled visit will be used for efficacy analyses. For safety analyses, the results from scheduled visit will be used first, if no scheduled visit, the record from the visit closest to target date will be used. If there are multiple records with the same distance to the target date, the latest record will be used.

If the final on-treatment safety assessments are repeated or unscheduled, the last post-baseline assessment will be used as the final on-treatment assessment for generating descriptive statistics.

However, all post-baseline assessments will be used for PCI value determination and all assessments will be presented in the data listings.

26Jul2018

Page 33 of 43

